3.2. SECONDARY OBJECTIVES

The secondary objectives are to evaluate the effects of the three sequencing combination treatments on:

- Total Progression-Free Survival (PFS);
- 3 years PFS rate;
- Percentage of patients alive at 3 years;
- Best overall response rate (BORR);
- Duration of response (DoR);
- Toxicity of the investigational medicinal products (IMPs);
- Quality of life and general health status defined by:
 - Health-related quality of life (HRQoL), by means of the 30-item European Organisation for Research and Treatment of Cancer quality of life questionnaire (EORTC QLQ-C30);
 - General health status, by means of the European Quality of Life 5-Dimensions (EQ-5D) questionnaire;
 - Impairment of work productivity and activity, by means of the Work Productivity and Activity Impairment: General Health (WPAI:GH) questionnaire.

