9. STATISTICAL CONSIDERATIONS

9.1. ADJUSTMENTS FOR COVARIATES AND FACTORS TO BE INCLUDED IN ANALYSES

The following adjustment for covariates is planned for this study.

The Cox's Proportional Hazards regression model on Overall Survival, Total Progression Free Survival and Duration of Response will include as covariates:

- a) Treatment sequence assigned: Arm A, Arm B, Arm C;
- b) Age (years): continuous variable;
- c) Gender: Male and Female;
- d) Melanoma Type: Cutaneous, Mucosal, Ocular;
- e) Stage at current diagnosis: IIIa, IIIb, IIIc, IV – M1a, IV – M1b, IV – M1c;
- f) Baseline LDH level: continuous variable;
- g) ECOG PS at baseline: 0, ≥ 1 ;

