9.3. MISSING DATA

Any Missing data will not be imputed (including efficacy data).

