20.2.1. SECONDARY EFFICACY VARIABLES & DERIVATIONS

The secondary efficacy endpoints are:

- a) Total PFS, calculated from the date of randomization until the date of the second progression (i.e., the progression to second treatment); any progression or death will be considered as an event if patient cannot complete treatment sequence.
 Any patient not known to have experienced progression or died at the time of data analysis will be censored at the time of the last recorded date on which the patient was known to be alive without disease progression.
 Total PFS (months) = [(Date of second progression or any progression/death or last contact – date of randomization +1)/30.4]
- b) 3 years PFS rate (PFSR), calculated from the date of randomization until the date of progression or death from any cause. This rate estimates the proportion of patients who did not progress and were alive 3 years after randomization.
- c) Percentage of patients alive at 2 and 3 years;
- d) Best overall response rate (BORR), defined as the best response designation, as determined by the investigator, recorded between the date of randomization and the date of objectively documented progression per RECIST version 1.1 criteria;
- e) Duration of response (DoR), calculated as the time from the date of first documented response (CR or PR) until the date of the first documented progression or death due to

¹ where 0=censored; 1 = event.

underlying cancer. If a patient with a CR or PR has no progression or death due to underlying cancer, the patient is censored at the date of last adequate tumor assessment;

DoR (months) = $[(\text{Date of first documented progression/death due to underlying cancer or date of last tumor assessment} - \text{date of first CR or PR} + 1)/30.4]$

- f) Health-related quality of life (HRQoL), by means of the 30-item European Organisation for Research and Treatment of Cancer quality of life questionnaire (EORTC QLQ-C30);
- g) General health status, by means of the European Quality of Life 5-Dimensions (EQ-5D) questionnaire;
- h) Impairment of work productivity and activity, by means of the Work Productivity and Activity Impairment: General Health (WPAI:GH) questionnaire.

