20.2.2. ANALYSIS OF SECONDARY EFFICACY VARIABLES

The secondary efficacy analyses will be performed in ITT set.

The following statistical methods will be applied on the secondary efficacy endpoints:

- a) Total PFS: The estimates of the survivor function using the Kaplan-Meier approach will be displayed graphically by treatment arm. Median time and the corresponding two-sided 95% confidence interval will be presented together with the estimates for the other quartiles (SAS procedure PROC LIFETEST) by treatment arm separately.
 A Cox's proportional hazard regression model will also be performed to assess the influence of some baseline covariates on total PFS. Covariates of interest are those reported in [Paragraph 9.1](#). Hazard ratios estimates with their 95% confidence limits will be also presented (SAS procedure PROC PHREG).
- b) 3-years PFSR: The PFSR at 3 years will be estimated by the Kaplan-Meier method. The 95% confidence intervals for the PFSR will be estimated using Greenwood's estimate of the standard error (SE) and a linear transformation of the progression-free survival function.
- c) Percentage of patients alive at 2 and 3 years will be reported using Wilson score intervals for each treatment arm.
- d) BORR: Default summary statistics of the best overall response from the date of randomization to the date of objectively documented progression per RECIST version 1.1 criteria will be presented, by treatment arm.
 For each treatment arm, the Overall Response Rate (ORR) will be calculated as the percentage of patients in the ITT set who have a CR or PR before any evidence of progression (as defined by RECIST).
 A 95% confidence interval (CI) will be derived for the ORR using Wilson score intervals (CIs for a single proportion).
- e) The estimates of the survivor function of DoR using the Kaplan-Meier approach will be displayed graphically by treatment arm. Median time and the corresponding two-sided 95% confidence interval will be presented together with the estimates for the other quartiles (SAS procedure PROC LIFETEST) by treatment arm separately.
 A Cox's proportional hazard regression model will also be performed to assess the influence of some baseline covariates on DoR. Covariates of interest are those reported in [Paragraph 9.1](#). Hazard ratios estimates with their 95% confidence limits will be also presented (SAS procedure PROC PHREG).

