	Censored	n (%)	xx (xx.x)	xx (xx.x)	xx (xx.x)

Notes:

Duration of Response (DoR) is defined as the time from the date of first documented response (CR or PR) to the date of first documented progression or death due to underlying cancer;

DoR (months) = [(Date of first documented progression/death due to underlying cancer or date of last tumor assessment - date of first CR or PR +1)]/30.4.

If a patient with a CR or PR has no progression or death due to underlying cancer, the patient is censored at the date of last adequate tumor assessment.

Percentages are calculated relative to the total number of the patients in the ITT set by treatment arm.

DoR (months) will be estimated using Kaplan-Meier method.

Source: XXXX.SAS, Run on DDMMYYYY

TABLE 34. Analysis of Secondary Endpoint: Summary of Duration of Response (DoR) (cont.)

POPULATION: ITT

Arm A

[figure not shown]
Time Interval (months)	Censoring Indicator	Survival Distribution Function Estimate	Survival Standard Failure	Survival Standard Error	Number Failed	Number Left	SDF Lower 95% Confidence Limit	SDF Upper 95% Confidence Limit
x.xxxx	x	x.xxxx	x	x	x	xx	x.xxxx	x.xxxx
x.xxxx	x	x.xxxx	x	x	x	xx	x.xxxx	x.xxxx
x.xxxx	x	x.xxxx	x	x	x	xx	x.xxxx	x.xxxx
x.xxxx	x	x.xxxx	x	x	x	xx	x.xxxx	x.xxxx
x.xxxx	x	x.xxxx	x	x	x	xx	x.xxxx	x.xxxx
x.xxxx	x	x.xxxx	x	x	x	xx	x.xxxx	x.xxxx
x.xxxx	x	x.xxxx	x	x	x	xx	x.xxxx	x.xxxx
x.xxxx	x	x.xxxx	x	x	x	xx	x.xxxx	x.xxxx
x.xxxx	x	x.xxxx	x	x	x	xx	x.xxxx	x.xxxx

Source: XXXX.SAS, Run on DDMMYYYY

< Note for SAS Programmer: This must be produced for each arm separately >

TABLE 34. Analysis of Secondary Endpoint: Summary of Duration of Response (DoR) (cont.)

POPULATION: ITT

Source: XXXX.SAS, Run on DDMMYYYY

TABLE 35. Analysis of Secondary Endpoint: Predictive factors of Duration of Response

POPULATION: ITT

The PHREG Procedure

Model Information

Data Set	xxxx	
Dependent Variable	xxxx	Duration of Response (Months)
Censoring Variable	xxxx	Censor
Censoring Value(s)	0	
Ties Handling	BRESLOW	

Number of Observations Read	xxx
Number of Observations Used	xxx

Summary of the Number of Event and Censored Values

Total	Event	Censored	Percent Censored
xxx	xx	xx	xx.xx

Convergence Status

Convergence criterion (GCONV=1E-8) satisfied.

Model Fit Statistics

Criterion	Without Covariates	With Covariates
-2 LOG L	xxxx.xxx	xxxx.xxx
AIC	xxxx.xxx	xxxx.xxx
SBC	xxxx.xxx	xxxx.xxx

Testing Global Null Hypothesis: BETA=0

Test	Chi-Square	DF	Pr > ChiSq
Likelihood Ratio	xx.xxxx	xx	x.xxxx

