Score	xx.xxxx	xx	x.xxxx
Wald	xx.xxxx	xx	x.xxxx

Source: XXXX.SAS, Run on DDMMYYYY

Table 35. Analysis of Secondary Endpoint: Predictive factors of Duration of Response

POPULATION: ITT

The PHREG Procedure

Analysis of Maximum Likelihood Estimates								
Parameter	DF	Parameter Estimate	Standard Error	Chi-Square	Pr > ChiSq	Hazard Ratio	95% Confidence Interval	
							Lower	Upper
VAR1	x	x.xxxxx	x.xxxxx	x.xxxx	x.xxxx	x.xxx	x.xxx	x.xxx
VAR2	x	x.xxxxx	x.xxxxx	x.xxxx	x.xxxx	x.xxx	x.xxx	x.xxx
VAR3	x	x.xxxxx	x.xxxxx	x.xxxx	x.xxxx	x.xxx	x.xxx	x.xxx
VAR4	x	x.xxxxx	x.xxxxx	x.xxxx	x.xxxx	x.xxx	x.xxx	x.xxx
...								
VARn	x	x.xxxxx	x.xxxxx	x.xxxx	x.xxxx	x.xxx	x.xxx	x.xxx

Note for programming:

List of predictive factors to be included in the Cox's model:

- a) Treatment sequence assigned: Arm A, Arm B, Arm C;
- b) Age (years): continuous variable;
- c) Gender: Male and Female;
- d) Melanoma Type: Cutaneous, Mucosal, Ocular;
- e) Stage at current diagnosis: IIIa, IIIb, IIIc, IV - M1a, IV - M1b, IV - M1c;
- f) Baseline LDH level: continuous variable;
- g) ECOG PS at baseline: 0, ≥1;

Source: XXXX.SAS, Run on DDMMYYYY

TABLE 36. Analysis of Secondary Endpoint: Change from baseline of Health-Related Quality of Life (HRQoL) by means of EORTC-QLQ-C30 - ARM A

POPULATION: ITT

< Note for SAS Programmer: the following must be presented for each scale of the EORTC-QLQ-C30 >

	Statistic	Value	Change from Baseline (*)
Global Health Status / QoL			
Baseline 1	n	xx	
	Mean (SD)	xx.x (x.x)	
	Median	xx.x	
	Min/Max	xx/xx	
Week <Every 4 wks> - Combo Target	n	xx	xx
	Mean (SD)	xx.x (x.x)	xx.x (x.x)
	Median	xx.x	xx.x
	Min/Max	xx/xx	xx/xx
Baseline 2	n	xx	
	Mean (SD)	xx.x (x.x)	
	Median	xx.x	
	Min/Max	xx/xx	
Week <Every 3 wks x 4 times> - Nivolumab + Ipilimumab	n	xx	xx
	Mean (SD)	xx.x (x.x)	xx.x (x.x)
	Median	xx.x	xx.x
	Min/Max	xx/xx	xx/xx
Week <Every 4 wks> - Nivolumab	n	xx	xx
	Mean (SD)	xx.x (x.x)	xx.x (x.x)
	Median	xx.x	xx.x
	Min/Max	xx/xx	xx/xx
End of Treatment	n	xx	xx
	Mean (SD)	xx.x (x.x)	xx.x (x.x)
	Median	xx.x	xx.x
	Min/Max	xx/xx	xx/xx
Follow-up	n	xx	xx
	Mean (SD)	xx.x (x.x)	xx.x (x.x)
	Median	xx.x	xx.x
	Min/Max	xx/xx	xx/xx

Notes:

(*) Change from baseline is calculated relative to Baseline 1 for values between Baseline 1 and Baseline 2; Baseline 2 for values after Baseline 2. Change from baseline values include only those patients with both a Baseline value and a value for summarized time period. n represents number of patients contributing to summary statistics.

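### Duration of response is analysed among responders only, yet Tables 34 and 35 are headed ITT, print a non-randomised arm hazard ratio, and take event and censoring percentages over the wrong denominator

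*Supplement*

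**What the plan says.** - **Definition.** SAP Section 20.2.1 item e has DoR "calculated as the time from the date of first documented response (CR or PR) until the date of the first documented progression" or death from the underlying cancer. Section 9.3 rules out imputation, for efficacy data as well. A patient who never responds therefore has no DoR.
- **Model.** Section 20.2.2 item e plans Kaplan-Meier curves by arm and adds: "A Cox's proportional hazard regression model will also be performed to assess the influence of some baseline covariates on DoR". Section 9.1 gives one list for three endpoints: "The Cox's Proportional Hazards regression model on Overall Survival, Total Progression Free Survival and Duration of Response will include as covariates". Item a) is "Treatment sequence assigned: Arm A, Arm B, Arm C". The programming note to Table 35 ("List of predictive factors to be included in the Cox's model") repeats arm as item a), and the shell prints an HR, 95% limits and a p-value for every parameter.
- **Population.** Section 20.2.2 and both shells name the ITT set. Section 7 defines no responder set.
- **Denominator.** The note to Table 34 reads: "Percentages are calculated relative to the total number of the patients in the ITT set by treatment arm". It governs the rows for events and censored.
- **Purpose.** Section 3.2 introduces the list that contains DoR with "The secondary objectives are to evaluate the effects of the three sequencing combination treatments on". Section 8.3 says that no comparative tests between arms will be done and that results are descriptive.

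Table numbers here are those of the shells. The list of tables at the start of Section 26 numbers the same two outputs 32 and 33.

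**The concern.** The ITT heading is right for OS and total PFS, where every randomised patient contributes an event or a censored time. For DoR it is not. Patients enter the analysis because of something that happened after randomisation, and the three responder groups need not be comparable. An arm that brings only its best-prognosis patients to response can show longer DoR without longer disease control. A reader who sees an arm HR with a CI and p-value under an ITT heading, for an endpoint whose stated objective is the effect of the sequences, is likely to take it as a randomised contrast.

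The denominator is a separate and simpler matter. The percentage of responders censored tells the reader how mature the DoR curve is. Divided by all ITT patients, it mixes maturity with response rate, and arms with the same maturity look different.

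**Working it through.** **1. Design figures.** The plan states no figure for DoR. Its arm size does reproduce. With p0 = 0.33, p1 = 0.48 and success at 30 or more of 69 alive at 24 months, the exact binomial gives alpha 0.0446 and power 0.808. Sixty-nine is the smallest n meeting 5% and 80%, and 207/0.9 = 230. So n = 69 per arm is used below.

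**2. Table 34 denominator.** Let an arm have N patients, R responders, E events and C = R − E censored. As written, the table prints E/N and C/N, which sum to R/N, the response rate. With responders as denominator it would print E/R and C/R, which sum to 100%. Response rates and event counts below are assumed, because the SAP gives none by arm.

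| N | R | E | C | Printed (E, C) | Sum | Among responders (E, C) |
|---|---|---|---|---|---|---|
| 69 | 28 | 14 | 14 | 20.3%, 20.3% | 40.6% | 50.0%, 50.0% |
| 69 | 45 | 22 | 23 | 31.9%, 33.3% | 65.2% | 48.9%, 51.1% |

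Both arms are about half censored, but the printed values are 20.3% and 33.3%. Table 35 prints its own pooled percentage censored over the observations used. For these two arms alone that is (14 + 23)/(28 + 45) = 50.7%, which agrees with neither printed value.

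**3. Arm HR among responders, with identical PFS in both arms.** Taken from the plan: median PFS 10 months, first scan at 8 weeks (1.84 months). Assumed: exponential PFS; a response score correlated rho with PFS; response only if progression-free at the scan; DoR = PFS − 1.84 months, censored at 36 months; no covariate adjustment; 200,000 patients per arm. The HR is for the arm with fewer responders against the arm with more.

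| Response propensity | rho 0.3 | rho 0.5 | rho 0.7 |
|---|---|---|---|
| 65% v 55% | 0.960 | 0.942 | 0.906 |
| 65% v 50% | 0.943 | 0.896 | 0.851 |
| 70% v 50% | 0.926 | 0.878 | 0.819 |

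Equal propensities give about 1.00, and so does rho = 0 with unequal propensities.

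**4. A second model.** One normal prognostic factor drives both response and post-response hazard, with no arm effect on that hazard. The HR for the arm with more responders is 1.05 to 1.14 at 65% v 50% response, and 1.10 to 1.17 at 65% v 40%. Inverted to the orientation of step 3, that is 0.95 to 0.88 and 0.91 to 0.86. With equal response rates the HR is 0.99 to 1.01. With no shared factor it is 0.99 to 1.02. Direction and order of size agree with step 3.

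**5. Against the precision of this trial.** In the model of step 3 at 69 per arm, the standard error of the arm log HR is about 0.25. A true HR of 1 therefore carries a 95% CI of about exp(±1.96 × 0.25) = 0.61 to 1.63. The bias in log HR runs from |ln 0.960|/0.25 = 0.16 to |ln 0.819|/0.25 = 0.80 standard errors. The CI excludes 1 in about 6% to 7% of trials at 65% v 50% with rho 0.5, and in about 12% to 13% in the most extreme case, against 5% nominal.

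**The case against.** The strongest reply is that the plan does not present this as a comparison of arms. The Cox model is there to examine baseline covariates, Table 35 is titled as an analysis of predictive factors, Section 8.3 disclaims comparative tests, and no decision rests on DoR. That stands, and it limits the weight of the point. It does not remove the arm row from Table 35 or make it a randomised contrast.

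A reader might infer that the arm HR will be biased. The documents do not support that. Bias needs unequal response rates, and it needs shared causes of response and duration left over after adjustment for age, sex, melanoma type, stage, LDH and ECOG status. The SAP gives no response rate by arm, and the simulations leave out the planned adjustment, which would shrink the effect.

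A reader might also gauge the bias against the 15 and 23 month OS medians in Section 4.2. Those are the null and alternative for each single arm. They are not a between-arm effect and do not concern DoR, so they offer no yardstick.

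On the denominator, the shells print counts beside the percentages, the footnote discloses the base, and the Kaplan-Meier listings show numbers failed and left. A careful reader could recover maturity by arm. The printed percentages still mislead anyone who takes them at face value. ORR by arm, total PFS and the 3-year PFS rate, all in the full ITT set, already give context.

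**Conclusion.** The point holds in two parts of different strength.

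The Table 34 denominator is wrong as written, and this needs no assumption: the two percentages must sum to the response rate. The size depends on that rate. At 28 responders of 69, a half-mature curve prints as 20.3% censored.

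The ITT heading and the unlabelled arm HR in Table 35 misdescribe a responder-only analysis. This follows from the DoR definition and the absence of imputation; the SAP does not state the restriction itself. The bias is possible, not established: an HR of about 0.82 to 0.96 in favour of the arm with fewer responders, under assumed response rates and correlations without covariate adjustment. That is generally less than the sampling error at 69 per arm. The primary analysis and the sample size are unaffected.

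**What to change.** - Head Tables 34 and 35 *ITT patients with CR or PR*, and say so in Section 20.2.2 item e.
- Change the Table 34 note so that event and censored percentages are relative to the number of responders in each arm.
- Drop assigned arm from the DoR model in Section 9.1 and the Table 35 note. Alternatively keep it, with a footnote that its HR is a non-randomised comparison among responders.

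Optional: mean time in response in the full ITT set, counting non-responders as 0 months. This is a different estimand on which statisticians may disagree, and the point does not depend on it. Median DoR stays as the responder-only description.

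The cost is SAP wording, two table headings, a footnote and one line of model code. No new data are needed. If arm is dropped, the arm-adjusted estimates for the other covariates are lost; the footnote avoids that.

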- f) Default summary statistic of all scale scores of the EORTC QLQ-C30 and of the changes from baseline of each scale will be presented by treatment arm, according to the following scoring method.

For all the scales, the Raw Score (RS) is the mean of the component items:

$$RS = (I_1 + I_2 + \dots + I_n)/n.$$

A linear transformation to standardise the Raw Scores is used, so that scores range from 0 to 100; a higher score represents a higher (“better”) level of functioning, or a higher (“worse”) level of symptoms.

For Functional Scales, the transformation to be used is the following:

$$Score = \left\{ 1 - \frac{(RS - 1)}{range} \right\} \times 100$$

where range is the difference between the possible maximum and the minimum response to individual items.

For Symptoms scales/items and Global health status / QoL the transformation is the following:

$$Score = \left\{ \frac{(RS - 1)}{range} \right\} \times 100$$

The component items and the range which define each scale score are reported in the following table.

Table 2 Component items and range for EORTC QLQ-C30 scoring

	Scale	Number of items	Item range	Item numbers
Global health status / QoL	QL2	2	6	29,30
Functional scales				
Physical functioning	PF2	5	3	1 to 5
Role functioning	RF2	2	3	6, 7
Emotional functioning	EF	4	3	21 to 24
Cognitive functioning	CF	2	3	20, 25
Social functioning	SF	2	3	26, 27
Symptom scales / items				
Fatigue	FA	3	3	10, 12, 18
Nausea and vomiting	NV	2	3	14, 15
Pain	PA	2	3	9, 19
Dyspnoea	DY	1	3	8
Insomnia	SL	1	3	11
Appetite loss	AP	1	3	13
Constipation	CO	1	3	16
Diarrhoea	DI	1	3	17
Financial difficulties	FI	1	3	28

- g) The EQ-5D questionnaire consists of 5 5-levels items (mobility, self-care, usual activities, pain/discomfort, anxiety/depression) and of the EQ Visual Analogue Scale (EQ VAS). The digits for 5 dimensions can be combined in a 5-digit number describing the respondent’s health state (11111 indicates no problems, while 55555 indicates severe problems in all the 5 dimensions). Missing values can be coded as 9. Ambiguous values should be treated as missing values. Health states will be converted into a single index values by using the UK TTO value set. Default summary statistics and changes from baseline of the EQ-5D index will be presented by treatment arm.
- h) The following percentages will be calculated for each patient at each of the foreseen administrations. Default summary statistics and changes from baseline of these 4 scores will be presented by treatment arm.

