- Percent work time missed due to health: $Q2/(Q2+Q4) \times 100$;
 - Percent impairment while working due to health: $Q5 \times 10$;

- Percent overall work impairment due to health: $\{Q2/(Q2+Q4) + [(1-(Q2/(Q2+Q4))) \times (Q5/10)]\} \times 100$
- Percent activity impairment due to health: $Q6 \times 10$.

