Notes:

(*) Change from baseline is calculated relative to Baseline 1 for values between Baseline 1 and Baseline 2; Baseline 2 for values after Baseline 2. Change from baseline values include only those patients with both a Baseline value and a value for summarized time period.
n represents number of patients contributing to summary statistics.

Source: XXXX.SAS, Run on DDMMYYYY

TABLE 43. Analysis of Secondary Endpoint: Change from baseline of Impairment of work productivity and activity by means of WPAI:GH - ARM B

POPULATION: ITT

< Note for SAS Programmer: the following must be presented for each scale of the WPAI:GH >

	Statistic	Value	Change from Baseline (*)
Percent work time missed due to health			
Baseline 1	n	xx	
	Mean (SD)	xx.x (x.x)	
	Median	xx.x	
	Min/Max	xx/xx	
Week <Every 3 wks x 4 times> - Nivolumab + Ipilimumab	n	xx	xx
	Mean (SD)	xx.x (x.x)	xx.x (x.x)
	Median	xx.x	xx.x
	Min/Max	xx/xx	xx/xx
Week <Every 4 wks> - Nivolumab	n	xx	xx
	Mean (SD)	xx.x (x.x)	xx.x (x.x)
	Median	xx.x	xx.x
	Min/Max	xx/xx	xx/xx
Baseline 2	n	xx	
	Mean (SD)	xx.x (x.x)	
	Median	xx.x	
	Min/Max	xx/xx	
Week <Every 4 wks> - Combo Target	n	xx	xx
	Mean (SD)	xx.x (x.x)	xx.x (x.x)
	Median	xx.x	xx.x
	Min/Max	xx/xx	xx/xx
End of Treatment	n	xx	xx
	Mean (SD)	xx.x (x.x)	xx.x (x.x)
	Median	xx.x	xx.x
	Min/Max	xx/xx	xx/xx
Follow-up	n	xx	xx
	Mean (SD)	xx.x (x.x)	xx.x (x.x)
	Median	xx.x	xx.x
	Min/Max	xx/xx	xx/xx

Notes:

(*) Change from baseline is calculated relative to Baseline 1 for values between Baseline 1 and Baseline 2; Baseline 2 for values after Baseline 2. Change from baseline values include only those patients with both a Baseline value and a value for summarized time period.

n represents number of patients contributing to summary statistics.

Source: XXXX.SAS, Run on DDMMYYYY

TABLE 44. Analysis of Secondary Endpoint: Change from baseline of Impairment of work productivity and activity by means of WPAI:GH - ARM C

POPULATION: ITT

< Note for SAS Programmer: the following must be presented for each scale of the WPAI:GH >

	Statistic	Value	Change from Baseline (*)
Percent work time missed due to health			
Baseline 1	n	xx	
	Mean (SD)	xx.x (x.x)	
	Median	xx.x	
	Min/Max	xx/xx	
Day 1 - Combo Target	n	xx	xx
	Mean (SD)	xx.x (x.x)	xx.x (x.x)
	Median	xx.x	xx.x
	Min/Max	xx/xx	xx/xx
Week 4 - Combo Target	n	xx	xx
	Mean (SD)	xx.x (x.x)	xx.x (x.x)
	Median	xx.x	xx.x
	Min/Max	xx/xx	xx/xx
Baseline 2	n	xx	
	Mean (SD)	xx.x (x.x)	
	Median	xx.x	
	Min/Max	xx/xx	

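### If Q5 is blank when no hours were worked, the WPAI overall work impairment formula gives missing where its only possible value is 100%

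*Supplement*

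**What the plan says.** SAP section 20.2.2 item h defines four WPAI:GH scores and introduces them with "The following percentages will be calculated for each patient at each of the foreseen administrations". No employment condition or skip condition is attached. Three of the four matter here:

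- "Percent work time missed due to health" is Q2/(Q2+Q4) x 100.
- "Percent impairment while working due to health" is Q5 x 10.
- "Percent overall work impairment due to health" is {Q2/(Q2+Q4) + [(1 - Q2/(Q2+Q4)) x Q5/10]} x 100.

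The fourth score, activity impairment, uses Q6 alone. Item h has no rule for Q4=0, for a blank Q5 or for Q2+Q4=0. Item g, by contrast, does say how missing and ambiguous EQ-5D answers are handled.

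Section 9.3 states "Any Missing data will not be imputed (including efficacy data". Sections 5.3 and 8.5 specify SAS. The WPAI table shells add that "Change from baseline values include only those patients with both a Baseline value and a value for summarized time period" and that "n represents number of patients contributing to summary statistics".

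**The concern.** A patient who worked no hours has nothing to rate under an item about impairment while working, so a blank Q5 is plausible. The printed formula still multiplies by Q5, and in SAS arithmetic zero times missing is missing. The score then disappears for someone whose overall work impairment is fully determined by Q2 and Q4.

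The loss is not random. Every score lost this way equals 100, the top of the scale, so the mean of the remaining scores understates impairment. The outputs would also disagree with each other: Listing 38 would show the same patient at 100% work time missed with an empty overall work impairment cell, and the two scores would be summarised on different sets of patients.

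**Working it through.** The plan states no figure for this point, so there is nothing to reproduce. The check evaluates the printed formula.

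**Inputs.** The formulas come from section 20.2.2 item h. Reading Q2 as hours missed and Q4 as hours worked is inferred from the score labels, since the SAP does not define the items.

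**Step 1: ordinary cases.** Write a = Q2/(Q2+Q4), so that the score is {a + (1 - a) x Q5/10} x 100.

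- Q2=20, Q4=20, Q5=5: a = 0.5, and 0.5 + 0.5 x 0.5 = 0.75, giving 75%.
- Q2=0, Q4=40, Q5=3: a = 0, and 0 + 1 x 0.3 = 0.3, giving 30%.

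The formula behaves as intended here.

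**Step 2: Q2>0, Q4=0, Q5 answered.** Now a = 1 and 1 - a = 0, so the score is {1 + 0 x Q5/10} x 100 = 100%. This was evaluated at Q2 = 1, 8, 20 and 40 for every Q5 from 0 to 10, and the result was 100% each time.

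**Step 3: Q2>0, Q4=0, Q5 blank.** The second term is 0 x missing, which is missing, so overall work impairment is missing at all four Q2 values. Work time missed is still 100%. Impairment while working is missing too, but that is appropriate, because there is nothing to rate.

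**Step 4: Q2+Q4=0.** The ratio is 0/0, so both scores that use hours are undefined. The SAP does not say so.

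**Step 5: size in the mean.** Let f be the share of employed respondents in the Step 3 position and m the mean score of the others. The plan reports m. The correct mean is (1 - f) x m + f x 100. The shortfall is therefore f x (100 - m). Neither f nor m is in the documents, so both are assumed over a range:

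| f | m = 20 | m = 30 | m = 50 |
|---|---|---|---|
| 5% | 4.0 | 3.5 | 2.5 |
| 10% | 8.0 | 7.0 | 5.0 |
| 20% | 16.0 | 14.0 | 10.0 |
| 30% | 24.0 | 21.0 | 15.0 |

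For example, with f = 10% and m = 30 the reported mean is 30, while the correct one is 0.9 x 30 + 0.1 x 100 = 37.

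**Step 6: change from baseline.** Section 8.4 resets the baseline at each treatment block, and both values must be present. A patient moving from 20% to total absence loses a change of +80. A patient totally absent at Baseline 2 who later scores 20% loses a change of -80. A patient absent at both visits loses a change of 0. The direction of the net effect is not fixed.

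**The case against.** The strongest objection is that the formula is not wrong in itself. It returns 100% for any answered Q5, and nothing in the documents shows that Q5 is skipped when no hours are worked. The questionnaire is not reproduced, and Listing 38 shows only the items and scores. This stands: the defect is conditional on a blank Q5, and that must be stated as an assumption.

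Three stronger readings are tempting and are not supported:

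- A reader might infer that section 9.3 forbids the repair. It does not. With Q2>0 and Q4=0 the score is fixed by recorded answers, so assigning 100 is a derivation and not an imputation. A programmer could already code it that way, and the SAP gives no WPAI code that says otherwise. Equally, nothing in the SAP tells the programmer to do so.
- A reader might infer that the worst-affected patients vanish from the WPAI results. They lose one score that they should have. Work time missed still shows them at its maximum, and Q6 still supplies activity impairment. The tables give n for each score and visit, so the loss could be seen.
- A reader might infer that change from baseline systematically hides deterioration, or that one arm gains. Step 6 shows that improvements can be lost as well, and the documents give no rates of total absence by arm.

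It is also fair to say that the endpoint listed in section 20.2.1 is work productivity and activity impairment as a whole. Overall work impairment is one of its four scores, and section 8.3 rules out comparative tests between arms.

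**Conclusion.** The point holds as a conditional one. If Q5 is blank for a patient with Q2>0 and Q4=0, the printed formula yields missing where the only possible value is 100%. The mean of overall work impairment is then biased toward less impairment by f x (100 - m), roughly 2.5 to 24 points over the assumed ranges f = 5-30% and m = 20-50. The direction of that bias is certain under the premise. Its size is illustrative, and the direction for change from baseline is not established. If Q5 is in fact always answered, the formula already gives 100% and nothing is lost.

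This is a minor correction to one descriptive secondary sub-score. It does not touch the overall survival analysis or the 24-month decision rule.

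**What to change.** Add to section 20.2.2 item h:

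- If Q2>0 and Q4 is recorded as 0, set percent overall work impairment to 100. Leave percent impairment while working missing if Q5 is blank.
- If Q2+Q4=0, set percent work time missed and percent overall work impairment to missing.
- Note that the first rule is a derivation from answered items and so is consistent with section 9.3.

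A blank Q5 with Q4>0 stays missing, as now. The rule is safe whether or not the blank-Q5 assumption holds, because it returns the formula's own value when Q5 is answered. It should be written in before database lock so that it is not left to a programming choice. The cost is a short addition to the text and one conditional statement, using items already collected.
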